The protocol, informed consent form(s), recruitment materials, and all participant materials will be submitted to the Institutional Review Board (IRB) for review and approval. Approval of both the protocol and the consent form must be obtained before any participant is enrolled. Any amendment to the protocol will require review and approval by the IRB before the changes are implemented to the study. In addition, all changes to the consent form will be IRB-approved; a determination will be made regarding whether a new consent needs to be obtained from participants who provided consent, using a previously approved consent form.

1 PROTOCOL SUMMARY

1.1 SYNOPSIS

Title	NIcotinamide Riboside in SARS-CoV-2 pAtients for reNAl protection (NIRVANA)			
Study Description	A pilot, double-blind, placebo-controlled, multicenter, interventional clinical trial with oral nicotinamide riboside (NR) 500 mg (versus placebo) twice daily for a total of 10 days in hospitalized participants with COVID-19.			
Objectives	Primary			
	 To determine the effect of nicotinamide riboside (NR) on whole blood NAD+ levels in hospitalized patients with COVID-19 infection and AKI during the 10-day intervention period; To evaluate the safety of NR in patients with COVID-19 infection and AKI during the 10-day intervention period; 			
	Secondary			
	 To determine the effect of NR on changes in area under curve (AUC) serum creatinine from baseline during the 10-day intervention; To determine the effects of NR on serum creatinine AUC, dialysis, and death with an ordinal categorical outcome having four categories (labeled 1, 2, 3, 4), defined as, in order from least to most severe disease, 1. Serum creatinine AUC < median, 2. Serum creatinine AUC ≥ median, 3. Dialysis, 4. Death during the 90d period post randomization; To determine the effect of NR on MAKE (Major Adverse Kidney Events; composite criteria defined as development or progression of chronic kidney disease, the initiation of long-term dialysis, or death from any cause) at 30d and 90d post randomization; To determine the effect of NR on degree of kidney impairment defined with estimated glomerular filtration rate (eGFR) and proteinuria at 30d and 90d post randomization; 			
	Exploratory			
	• To determine the relationship of whole blood NAD+ levels with AUC creatinine and surrogate markers of AKI such as kidney injury molecule- 1 (KIM-1) and neutrophil gelatinase-associated lipocalin (NGAL);			
Endpoints	Primary			
	 Rates of change in whole blood NAD+ level from baseline to day 10 in NR compared to Placebo. Safety of NR in hospitalized patients with COVID-19 and AKI (defined as the occurrence of at least one serious adverse event of grade 3 or higher or the occurrence of thrombocytopenia (>25% decline in blood platelet count from baseline value). 			

	Secondary				
	 Rates of change in AUC serum creatinine benchmarked to baseline from baseline to day 10 in NR compared to Placebo; An ordinal categorical outcome with four categories (labeled 1, 2, 3, 				
	4), defined as, in order from least to most severe disease, 1. Serun creatinine $AUC < median$, 2. Serum creatinine $AUC \ge median$, 3. Dialysis, 4. Death;				
	• Time to first occurrence of MAKE (doubling of serum creatinine, the initiation of long-term dialysis, or death from any cause) at 30 d and 90 d post randomization;				
	• Kidney function defined by eGFR and proteinuria at 30d and 90d post randomization.				
	Exploratory				
	• Correlations between whole blood NAD+, AUC serum creatinine, and AKI surrogate markers of AKI such as KIM-1 and NGAL;				
Study Population:	Participants will be >18 years old and admitted to hospital with a laboratory diagnosis of COVID-19 infection and AKI				
Phase:	Phase 2				
Description of	The study is a multicenter study with University of Texas Health San Antonio				
Sites/Facilities	(UTHSA) as the coordinating site. The three recruiting sites are: University				
Enrolling	Hospital affiliated with UTHSA, Icahn School of Medicine at Mount Sinai,				
Participants:	New York, NY and Harborview Medical Center/University of Washington, Seattle, WA				
Description of	The intervention for this clinical trial is Niagen®, a nicotinamide riboside,				
Study	an over the counter nutritional supplement				
Intervention:					
Study Duration	Estimated 2 years				
Participant	The estimated time required for this study will be up to 90 days after				
Duration:	consenting to study protocol. A total of up to 10 visits will occur during the				
	initial 10 days with two follow-up visits -30 days and 90 days from				
	enrollment date.				

1.2 SCHEMA

Flow diagram of the NIRVANA Study

COVID, Corona virus disease; EHR, Electronic health records; NR, Nicotinamide Riboside

1.3 SCHEDULE OF ACTIVITIES (SOA)

Table 1. Schedules of activities

Study Period \Rightarrow	Scree	Treatment Period					Follow-up						
Visit Encounter \Rightarrow	Visit	Visit	Visit	Visit	Visit	Visit	Visit	Visit	Visit	Visit	Visit	Visit	Visit
Procedure	0/	1/	2/	3/	4/	5/	6/	7/	8/	9/	10/	11/	12/
Troccuure	Day	Day	Day	Day	Day	Day	Day	Day	Day	Day	Day	Day	Day
	0	1	2	3	4	5	6	7	8	9	10	$30\pm$	90
		(Base line)*										3	±3
Eligibility criteria	Х												
Informed consent	Х												
Demography	Х												
Medical history	Х												
Concomitant	Х	Х	Х	Х	Х	Х	Х	Х	Х	Х	Х	Х	Х
medications ¹													
Vital signs		Х	Х	Х	Х	Х	Х	Х	Х	Х	Х	Х	Х
Physical	Х	Х	Х	Х	Х	Х	Х	Х	Х	Х	Х	Х	Х
examination													
STUDY INTERVEN	TION												
Randomization ²		Х											
Study drug		Х	Х	Х	Х	Х	Х	Х	Х	Х	Х		
administration ³													
STUDY PROCEDU	RES												
APACHE-II	Х	Х	Х	Х	Х	Х	Х	Х	Х	Х	Х		
Endpoint		Х	Х	Х	Х	Х	Х	X	X	Х	Х	Х	Х
assessment													
AE assessment		Х	Х	Х	Х	Х	Х	Х	Х	Х	Х	Х	Х
Respiratory	Х	Х	Х	Х	Х	Х	Х	Х	Х	Х	Х		
parameters ⁴													
Mortality, ICU	Х	Х	Х	Х	Х	Х	Х	Х	Х	Х	Х	Х	Х
transfer, length of													
stay													
Urine output ⁵		Х	Х	Х	Х	Х	Х	Х	Х	Х	Х		
CLINICAL LABOR	ATORY	7									-	-	
Blood analysis ⁶		Х	Х	Х	Х	Х	Х	Х	Х	Х	Х	X	X₽
SAFETY LABORA	ΓORY												
Blood analysis ⁷		Х	Х	Х	Х	Х	Х	Х	Х	Х	Х	Х	Х
RESEARCH LABO	RATOR	Y and R	EPOSI	TORY									
Blood and urine ⁸		Х	Х	Х	Х	Х	Х	Х	Х	Х	Х	Х	Х

APACHE-II, Acute physiology and chronic health evaluation II; AE, adverse events; ICU, Intensive care unit;

* Baseline (Day 1) assessments should be performed prior to study drug administration;

¹ Includes all inhospital and home medications (standard of care treatment, prescription, over-the-counter, supplements);

²Dosing of the first study drug will be administered as soon as possible (within 6 hours of obtaining consent and negative pregnancy test for women with childbearing potential);

³ Participants who will be discharged or leave hospital before Day 10 intervention will be provided with study pills for the remaining days.

⁴ Respiratory rate, FiO₂, O₂ saturation, ventilator parameters, if applicable and participant is hospitalized;

⁵ Urine output data based on medical records or from first morning urine collections if discharged from hospital;

⁶Any laboratory tests performed as part of routine clinical care within the specified visit day may be used for safety laboratory testing by extracting values from the EHR;

⁷ Creatine phosphokinase and liver function tests will be performed on Day 5 (see Table 4) ⁸ Whole blood NAD+ and serum creatinine will be collected daily before study medication dosing; Blood will be collected at 3-hour and 6-hour post-randomization for future pharmacokinetics; Blood and urine for biomarkers will be collected at Baseline and daily during the intervention period, at day 30 ± 3 and day 90 ± 3 ; [¶]If the participant is still hospitalized then inpatient safety laboratory test results will be collected from EHR

2 INTRODUCTION

2.1 STUDY RATIONALE

Impaired mitochondrial function has been recently recognized as a major mechanism for acute kidney injury (AKI) in septic shock and ischemia-reperfusion injury [1-5]. A major feature that limits mitochondrial function is the reduction of electron donors to the mitochondria in the form of nicotinamide adenine dinucleotide (NAD+). Reduced levels of NAD+ have been implicated in both animal models and humans with AKI, and stimulation of pathways that lead to enhancement of NAD+ appears to be beneficial [3, 4, 6]. Recent studies using oral nicotinamide (NAM) and nicotinamide riboside (NR) as NAD+ donors have found these agents to be safe, well-tolerated, and upregulate NAD+ pathways in a dose-dependent manner [7, 8]. NR provided *after* organ injury was found to be protective in pre-clinical studies [9, 10]. It has been demonstrated that NR is more orally bioavailable than NAM, safe in obese participants, and beneficial in many pre-clinical models of organ dysfunction [7, 8, 11-14]. NAM use during the perioperative period in participants undergoing cardiothoracic surgery showed reduced incidence of AKI in a pilot study [5]. NR use (in combination with pterostilbene, PT; NRPT) was found to increase NAD+ levels in patients with AKI as compared to the placebo group [15].

The kidneys are highly active metabolically, contain a high density of mitochondria, and consume the highest amount of oxygen after the heart. Mitochondrial energy (adenosine triphosphate or ATP) production requires the universal cofactor nicotinamide adenine dinucleotide (NAD). This essential metabolite serves as a key cofactor in a plethora of mitochondrial metabolic processes that facilitate energy production as well as several other important cellular functions [16]. Consistent with these key roles of NAD+, various stressors have been associated with decreased NAD+ levels [15], contributing to disease pathogenesis.

Rationale for Study Design:

We chose a treatment protocol with NR as a treatment for patients who will be admitted with COVID-19 related illness and develop AKI after admission. Treatment duration will be for 10 days and the primary study endpoint will be the change in whole blood NAD+ from baseline (to 10d, 2d, AUC) in NR group vs placebo group. We will evaluate whole blood NAD+ levels as a marker of efficacy and biological effect of NR based on two recent publications [8, 15]. We evaluated using a marker of efficacy for NR with the whole blood NAD+ based on two recent publications [8, 15]. In a study of healthy overweight subjects 40-60 years of age, Conze et al.

[8] found a 21 µg/ml mean NAD+ difference between patients randomized to 1000 mg NIAGEN[®] versus those randomized to placebo at day 7 (NIAGEN 42 µg/ml, Placebo 21 µg/ml) with a standard deviation of 10 µg/ml and approximately equal baseline means (NIAGEN 21 µg/ml, Placebo 24 µg/ml). Simic et al. [15] assessed a combination of NR with pterostilbene (NRPT) vs placebo in hospitalized patients of age \geq 18 years with AKI and found an 18% increase in whole blood NAD+ within 48h post treatment in the NRPT group, and a 50% reduction from baseline in the placebo group with AKI. With reference to Conze et al. [8] al., this study will achieve >99.9% power for testing H₀:R_{NR} = R_{Placebo} versus Ho: R_{NR} ≠ R_{Placebo} with alpha=0.05, autocorrelation (ρ)=0.5, and n=40 per arm where R_{NR} and R_{Placebo} are the rates of change from baseline to day 10 in the NR and Placebo arms, if the effects observed in this study are the same as those observed by Conze et al. with regard to NAD+. In this setting the effect size is 2.1 [=(42-21)/10] and the minimally detectable effect size is 0.63.

Safety of NR will also be assessed as a primary endpoint in this study. Although NR is generally recognized as safe or GRAS [17] and has been demonstrated to be well-tolerated with mild, if any side effects, reported using variables doses from 100 mg/day up to 2000 mg/day [8, 11, 12] it will be informative to assure that serious adverse events (SAEs) are not increased with NR in patients with COVID-19 infection and AKI.

We also plan to assess the AUC of serum creatinine benchmarked to baseline and other clinical outcomes as secondary endpoints to determine if there are trends indicating that NR may be a promising treatment for hospitalized COVID-19 infected patients who develop AKI. We will also correlate whole blood NAD+ levels with AUC creatinine with well described surrogate markers of AKI (KIM-1, NGAL) as an exploratory outcome measure. If we demonstrate that NR increases whole blood NAD+ in COVID-19 positive patients with AKI and is safe, this result would be a compelling finding to support further clinical trials with NR in this population. Further support for future studies would be obtained from our secondary endpoints and will of great value in establishing power calculations for future definitive studies [9, 10].

Upon completion of the NRIVANA study, we plan to pursue a Phase IIb or Phase III study based on the following scenarios:

- 1. Demonstrate significant increase in whole blood NAD+ level in the NR group compared to placebo (p<0.05), no significant increase in harm with NR treatment and a positive trend or improvement in any one of the secondary outcomes (p<0.2) would warrant a future Phase III study.
- 2. Demonstrate significant increase in whole blood NAD+ level in the NR group compared to placebo (p<0.05) and no significant increase in harm with NR treatment would warrant a Phase IIb study.
- 3. Demonstrate significant improvement in any one of the secondary outcomes with NR compared to placebo (p<0.2) and no significant increase in harm with NR treatment would warrant a Phase IIb study.

In a future Phase III clinical trial, we envision the primary endpoint would be the MAKE (Major Adverse Kidney Events) – the proportion of subjects who develop any of the components of MAKE at d90 post randomization. In the NIRVANA study MAKE is one of the secondary endpoints.

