5.5 STRATEGIES FOR RECRUITMENT AND RETENTION

Participants will be recruited from three participating sites: the University of Texas Health San Antonio (UTHSA), Icahn School of Medicine at Mount Sinai, New York, NY, and University of Washington (UW), Seattle, WA. The single IRB (sIRB) at the Washington University in St. Louis (FWA00002284) will serve as the Central IRB for all three participating sites. We will recruit and consent eligible participants and will advance them into the Treatment Period. A total of 100 participants will be randomized.

Each participating site and the coordinating site (UTHSA) will contribute to recruitment of study participants. Recruitment methods will focus primarily on the selection of eligible participants via identifying patients admitted to the respective hospitals with a diagnosis of COVID-19. Lead investigators at each site are physician scientists who will have direct access to eligible participants. For efficient recruitment, each site will employ the following approaches. After a COVID-19 patient is admitted to the hospital with a new positive laboratory diagnosis of COVID-19, the study team members will be notified by the COVID-19 Admitting Team. All

three participating sites also maintain a COVID-19 database which is updated every 6-8 hours and a designated study member will review the COVID-19 database twice a day. Each study team will have access to the respective hospital COVID-19 admission logs and EHR enabling them to review several eligibility criteria. The study investigators or clinical coordinators will approach the potentially eligible participants or LAR (when appropriate) and inform them of the study protocol. All participants will provide written consent for participation in the study. Sites have the ability to use one of the FDA approved options for obtaining written signature during a pandemic, based on their institutional requirements.

During consenting process, each participant will receive clear and detailed information about the NIRVANA study with an emphasis on risks, benefits, and alternative to enrollment. Participants will be given opportunities and time to learn about ongoing clinical trials for COVID-19 and their eligibility to enroll in another competing study. Voluntary participation will be discussed and participants will be allowed to withdraw from the current study at any time point after providing consent.

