6 STUDY INTERVENTION

6.1 STUDY INTERVENTION(S) ADMINISTRATION

6.1.1 STUDY INTERVENTION DESCRIPTION

Baseline Visit (Day 1)

After obtaining consent, baseline visit procedures will be performed as listed in Table 1 (Schedules of Activities in Section 1.3). Participants will be randomized after abstracting the following data from the EHR: sociodemographic, contact information, medical/surgical history,

comorbidities, and routine medications on admission, standard of care at hospital, home medications, all concomitant medicines including dietary or nutritional supplements and over-the-counter medications, vitals and physical examinations, routine laboratory test results.

Randomization will be accomplished through the use of an online randomization service. Participants will be randomly allocated to 1:1 ratio to receive either nicotinamide riboside (NR) or placebo. Only the study statisticians (Drs [name] and [name]) and the local hospital Research Pharmacists will have access to the randomized assignment for the purpose of tracking randomization and study drug dispensing, respectively. Study investigators and study participants will be blinded to the intervention assignments. Neither the statisticians nor the pharmacist will have direct contact with the study participants.

Eligible study participants enter intervention phase after consenting to the study protocol:

- Nicotinamide riboside (NR, Niagen[®]) or placebo will be administered orally (or via nasogastric tube) 500 mg twice a day for 10 days during hospitalization or prescribed for at home administration if discharged before 10 days from the hospital.
- Placebo capsule manufactured by ChromaDex to match NR or Niagen®

TREATMENT PERIOD

All measures related to study treatment visits are harmonized to standard of care to minimize care interruption and disruption to hospital staff workflow. Most of the treatment procedures are standard of care or routine procedures for COVID-19 participants in an acute care setting. These data will be obtained from the EHR. If any treatment procedure is not available through the EHR, the study team will obtain these data from the primary care team or directly from the participant. Where multiple results are present in the EHR, they will all be recorded in the study database so that all relevant values are captured. A summary of the trial's schedule of event is included in Table 1 (Section 1.3).

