Potential participants who may have severe AKI or advanced CKD will be considered with a binary independent variable in the models addressing this condition with corresponding displays of the line and whisker plots by treatment group and summary tables of coefficients, standard errors and p-values. Interactions between this binary variable and treatment will be of interest and will be described.

Capture and tabulation of concomitant medications, dialysis, co-enrollment in another COVID-19 clinical trial, any new standard of care, pre-existing CKD, and treatments by study arm (NR, Placebo) may be used to define other potential adjustments with binary or categorical variables to be defined post hoc in exploratory analyses. Such models may motivate extended interpretations of any treatment effects found.

PRIMARY END POINT: Safety

All reportable AEs will be listed by Preferred Term by subject, treatment, clinical site, grade, relation to treatment, severity, and seriousness. All unanticipated events will be listed by treatment and clinical site with a detailed description of each event, incident, experience or outcome. An unblinded statistician will summarize safety data periodically for the DSMB.

AEs will be tabulated by treatment and clinical site, displaying, for each event, the number and percentage of participants experiencing at least one Grade 3 or 4 occurrence and he null hypothesis to be tested is H_0 : $p_{NR}=p_{Placebo}$ where p_{NR} and $p_{Placebo}$ are the probabilities of experiencing at least one Grade 3 or Grade 3 event in the NR and Placebo groups. H_0 will be tested with Fisher's Exact test, overall and by clinical site. Additionally, treatment groups will be contrasted on the occurrence at least once of each event with Fisher's exact test. All statistical testing will be two-sided with a significance level of 5%.

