9.4.6 PLANNED INTERIM ANALYSES

An O'Brien-Fleming procedure will be used to conduct an interim analysis for safety when 50% of the patients complete the study. A statistical basis for stopping the study at the first look will be achieved if the test statistic for the primary safety endpoint (the occurrence of at least one serious adverse event of grade 3 or higher or the occurrence of thrombocytopenia less than 50,000 per microliter) indicates harm in the NR arm at p \leq 0.003. If the test statistic does not reach p \leq 0.003 at the first look then the trial will proceed to the final analysis. The statisticians (Drs. [name] and [name]) will inform the principal investigator if the interim analysis crosses the boundary in the direction of harm is observed (p \leq 0.003). A treatment effect will be declared harmful at the final analysis if the test statistic indicates harm and p \leq 0.047. The safety data will be summarized at interim analysis. The statisticians will inform the DSMB if there are any safety concerns at the interim analysis. Any decision on stopping the study based on safety will be made in coordination with NIDDK and the DSMB.

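### All three go scenarios accept a non-significant harm test as meeting the safety condition, which about 50 participants per arm cannot support

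*Combined protocol and SAP*

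**What the plan says.** Section 2.1 lists three scenarios for a Phase IIb or Phase III study, and each has a safety condition. Scenarios 2 and 3 end with "no significant increase in harm with NR treatment would warrant a Phase IIb study". Scenario 1, which leads to Phase III, uses the same condition. The paragraph before the list says that if NR raises NAD+ in these patients "and is safe, this result would be a compelling finding to support further clinical trials".

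The testing is described in two places. In Section 9.4.2 the null hypothesis of equal event probabilities "will be tested with Fisher's Exact test, overall and by clinical site", each event is also tested separately, and "All statistical testing will be two-sided with a significance level of 5"%. Section 9.4.6 says "A treatment effect will be declared harmful at the final analysis if the test statistic indicates harm and p" is at most 0.047, after an interim look at 0.003.

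On size, Section 5.5 states: "A total of 100 participants will be randomized". Section 6.1.1 states: "Participants will be randomly allocated to 1:1 ratio to receive either nicotinamide riboside (NR) or placebo". The only power statement (Sections 2.1 and 9.2) concerns NAD+. Section 9.4.1 plans 95% intervals for treatment effects where appropriate but does not link them to the go decision.

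**The concern.** Safety is one of two primary endpoints and a condition in every go scenario. The condition is met by failing to reject a null hypothesis of no difference, so a trial with little information on harm passes it readily. Nothing says how large an excess must be ruled out, or how precisely the excess must be estimated.

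The NAD+ condition is expected to be met almost surely if its planning assumption holds, since the stated power exceeds 99.9%. Scenario 2 then turns largely on the safety condition. In scenario 3 the only other condition is one secondary outcome at p<0.2. At stake is whether NR moves into larger trials in seriously ill patients with a safety statement that the data cannot carry.

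**Working it through.** **Inputs.** 100 randomized 1:1 gives 100/2 = 50 per arm (Sections 5.5 and 6.1.1). The safety population is everyone who received any study drug (Section 9.3), so close to 50 per arm. The test is two-sided Fisher at 0.05 (9.4.2) or 0.047 (9.4.6). The placebo rate of the safety endpoint is not given. The nearest figure is 9.9% mortality in Section 2.2 for patients meeting the entry criteria. The endpoint adds non-fatal serious events and platelet falls, so 20-50% is assumed, with 10% and 5% shown as well.

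**The plan's own figure.** For NAD+ with 40 per arm, the minimally detectable standardized effect at an assumed 80% power is (1.960 + 0.842) × √(2/40) = 0.626, which matches the stated 0.63. An effect of 2.1 gives power above 99.9%, as stated. There is no safety figure to reproduce.

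**Chance of passing the safety condition.** For each placebo rate p and true rise d, sum Bin(x; 50, p+d) × Bin(y; 50, p) over all pairs (x, y) for which Fisher p ≤ 0.05 with NR higher. The chance of passing is one minus that sum.

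| Placebo rate | +10 points | +20 points | +30 points |
|---|---|---|---|
| 5% | 75.6% | 25.2% | 3.2% |
| 10% | 80.5% | 36.0% | 7.3% |
| 20% | 84.5% | 48.5% | 14.7% |
| 30% | 86.9% | 53.7% | 17.1% |
| 40% | 86.7% | 53.8% | 17.1% |
| 50% | 86.7% | 53.7% | 14.7% |

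At 0.047, a 20-point rise at placebo rates of 20-50% passes in 50-54% of trials. Adding the interim look at 0.003 with 25 per arm leaves that range unchanged. For 80% power with 50 per arm, the true rise must be about 28-29 points at these placebo rates.

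**What a null-looking result leaves open.** With 20/50 in each arm, the Wilson interval for each rate is 27.6% to 53.8%. The Newcombe upper limit for the difference is √[(0.538 − 0.400)² + (0.400 − 0.276)²] = 0.186. The same calculation at observed rates of 20%, 30% and 50% gives 0.157, 0.175 and 0.189.

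**A result that would pass.** 30/50 on NR against 20/50 on placebo gives Fisher p = 0.071, although the observed excess is 20 points.

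**Two final levels.** 15/50 against 6/50 gives Fisher p = 0.0479. That is significant harm at 0.05 (9.4.2) and not at 0.047 (9.4.6), so identical data meet or fail the condition depending on the section applied.

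**Which event is tested.** Section 1.1 and Table 2 use a serious adverse event of grade 3 or higher, or a platelet fall of more than 25% from baseline. Section 9.4.2 tests Grade 3 or 4 occurrences. Section 9.4.6 uses a serious adverse event of grade 3 or higher, or platelets below 50,000 per microliter. The placebo rate, and so every row of the table, depends on which applies.

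**The case against.** The strongest reply is that this is a pilot, described as exploratory in Section 9.4.1, with 95% intervals planned and DSMB and NIDDK oversight in place. The go list is a planning statement, and two of its three scenarios lead to a further Phase II trial that can collect more safety data. That lowers the severity. It does not remove the problem, because neither the intervals nor the oversight is tied to the go list.

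Three stronger readings are tempting, and the documents do not support them.

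- A reader might infer that a 20-point rise passes about half the time whatever the background. That needs an assumed placebo rate. Section 8.3.6 exempts many illness outcomes from adverse event reporting unless they are judged related or of uncertain relationship, so a low recorded rate cannot be excluded.
- A reader might infer that the condition is easiest to pass when events are few. On the risk-difference scale the reverse holds here: a 20-point rise passes in 25% of trials at a 5% background and 54% at 30-50%. Fewer participants do make passing easier.
- A reader might infer that the plan formally defines non-significance as proof of safety. The scenarios say only that a further study would be warranted; the word safe stands in the preceding paragraph. The juxtaposition invites the inference, and the fix should block it.

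A reader might also conclude that a non-inferiority margin is essential. With a harmless drug, 50 per arm and rates of 20-50%, the Newcombe 95% upper limit falls below 10 points in only 18-23% of trials, below 15 in 33-47%, and below 20 in 54-71%. A tight margin would often stop a harmless drug, and a loose one still admits large harm.

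**Conclusion.** The point holds: the go list asks for the absence of a significant harm test, and at this size that does not support a statement that NR is safe. The pass probabilities describe the safety condition alone, not the whole go rule. They rest on 50 per arm and on a placebo rate that the documents do not supply. The logical gap does not depend on that rate; its size does. The two final harm levels and the differing endpoint definitions are contradictions in the text and need no assumption. Severity is should-fix: the defect affects the decision to proceed and the wording of the safety claim, not the conduct of this trial.

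**What to change.** In Sections 2.1 and 9.4.2, before any unblinded look:

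- Base the safety statement on the NR minus placebo risk difference for the single primary safety composite, with its 95% confidence interval and a named interval method. The method matters: for 30/50 against 20/50 the Newcombe interval is 0.5 to 37.5 points, which excludes zero although Fisher gives 0.071.
- State that a non-significant result means an excess up to the upper limit is not excluded, and do not call NR safe on that basis.
- State that the by-site and per-event Fisher tests do not enter the go decision.
- Use one final harm level in Sections 9.4.2 and 9.4.6.
- Reconcile the safety endpoint across Section 1.1, Table 2, Section 9.4.2 and Section 9.4.6.

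A formal margin agreed before unblinding is optional. It would change the decision materially and might call for a larger trial.

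The cost of the required changes is wording, with no new data or participants. The downside is a less favourable safety claim.
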